7.10. Other Safety Measures

A data listing will be provided for subjects who become pregnant during the study.

7.11. Changes From Protocol-Specified Safety Analyses

There are no deviations from the protocol-specified safety analyses.

8. PHARMACOKINETIC ANALYSES

8.1. Population PK Analysis

Population PK modeling will be applied on CCI [REDACTED] sparse PK samples to characterize the PK of SOF, GS-331007, VEL and VOX using mixed-effect modeling techniques. SOF, GS-331007, VEL and VOX exposures (AUC_{τ} , C_{\max} , and C_{τ} , if applicable) in pediatric subjects will be summarized using descriptive statistics (n, arithmetic mean, geometric mean and its 95% confidence interval, coefficient of variation [%CV], SD, median, Q1, Q3, minimum, and maximum), and will be compared with SOF/VEL/VOX adult populations. The primary PK endpoint of this analysis will be evaluated by carrying out an analysis of variance (ANOVA) for log-transformed SOF, GS-331007, VEL and VOX AUC_{τ} . The secondary PK endpoints of this analysis will be the C_{\max} and C_{τ} (if applicable), of SOF, GS-331007, VEL and VOX. The 90% confidence intervals will be constructed for the ratio of geometric means of each PK parameter. Population PK Analysis will be performed in ad hoc fashion upon estimated PK parameters using the population PK model are available.

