1.4. Rationale for Dose Selection of SOF/VEL/VOX FDC

SOF/VEL (400/100 mg) once daily is the approved marketed dose and, as such, was selected for co-formulation with VOX into a fixed dose combination tablet. The VOX 100 mg dose was selected based on the anti-HCV activity of VOX established in the Phase 1b proof-of-concept study GS-US-338-1121 and Phase 2 studies in subjects with HCV infection (GS-US-367-1169 and GS-US-367-1168). These studies indicated that the voxilaprevir exposures achieved following administration of VOX 100 mg + SOF/VEL (400/100 mg) with food are associated with > 90% of the maximum antiviral response across all HCV genotypes.

The combination of SOF 400 mg, VEL 100 mg, and VOX 100 mg has been administered in Phase 2 and Phase 3 studies to over 1900 subjects. SOF/VEL/VOX FDC (400/100/100 mg) tablet was evaluated in the registrational Phase 3 POLARIS program and these doses represent the marketed dose of SOF/VEL/VOX FDC tablet for the treatment of HCV-infection in adults.

Sofosbuvir is a substrate for efflux drug transporters P-glycoprotein (P-gp) and breast cancer resistance protein (BCRP). SOF is extensively metabolized to the pharmacologically active nucleoside analog phosphate. The activation pathway involves hydrolysis by intestinal and hepatically expressed carboxylesterase (CES1) and Cathepsin A (CatA) enzymes {[Yang 2009](#), [Zhu 2009](#)}. SOF is also converted to GS-331007, an inactive circulating metabolite, which is eliminated renally by active tubular secretion and glomerular filtration.

Velpatasvir is also a substrate for P-gp and BCRP. VEL has low systemic clearance in nonclinical species and low metabolic turnover by Cytochrome P450 2B6 (CYP2B6), Cytochrome P450 2C8 (CYP2C8) and Cytochrome P450 3A4 (CYP3A4). It is eliminated through biliary excretion as unchanged parent drug and metabolites (76.6% of the administered dose is recovered as VEL in feces).

Voxilaprevir is a substrate for P-gp, BCRP, and Organic Anion-Transporting Polypeptide (OATP) 1B1/3. VOX has low in vitro turnover, primarily by CYP3A4. It is eliminated through biliary excretion as unchanged parent drug and metabolites (40% of the administered dose is recovered as VOX in feces).

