8.5. Pharmacokinetic Analysis

Pharmacokinetic parameters (eg, AUC_{τ} , C_{\max} , C_{τ} , volume of distribution and clearance) will be listed and summarized for, SOF, its primary metabolite(s), VEL and VOX using descriptive statistics (eg, sample size, arithmetic mean, geometric mean, % coefficient of variation, standard deviation, median, minimum, and maximum).

To evaluate if the exposures of SOF, GS-331007, VEL and VOX achieved in pediatric subjects of this study are similar to the exposures observed in adult subjects, SOF, GS-331007, VEL and VOX exposure data from this study will be compared to the integrated adult data. The primary endpoint of this analysis will be evaluated by carrying out an analysis of variance (ANOVA) for log-transformed SOF, GS-331007, VEL and VOX AUC_{τ} . The 90% confidence intervals will be constructed for the ratio of geometric means of each PK parameters. The equivalence boundary is set as 50% to 200%. The equivalence boundary is based on exposure-response (efficacy and safety) relationships observed in the integrated adult data.

Dose ranging studies for SOF established that a dose of 200 mg results in suboptimal exposure compared to the 400 mg dose, and no clinically significant exposure-safety relationships were observed across a broad range of GS-331007 exposure. The Phase 1b dose ranging studies, GS-US-281-0102 and GS-US-338-1121, established the anti-HCV activity of VEL and VOX, respectively. At exposures observed in Phase 3 studies, maximum effect (E_{\max}) models predict near maximal antiviral activity for all analytes: 90%, $\geq 99.5\%$, $\geq 90\%$, of E_{\max} for SOF, VEL, and VOX, respectively.

In the Phase 3 population treated with SOF/VEL/VOX FDC (400/100/100 mg), virologic response rates were high across all treatment groups, HCV genotypes and exposure ranges for SOF, GS-331007, VEL and VOX, including for subjects with cirrhosis, with no consistent trends in exposure-efficacy relationships. Similarly, exposure-safety analyses in Phase 3 clinical studies showed a lack of relationship over a wide range of SOF/VEL/VOX FDC exposures. The observed safety and efficacy profile and the lack of exposure-response relationships across a wide range of SOF/VEL/VOX FDC exposures, the bounds of 50-200% support identification of a clinically relevant difference in SOF, GS-331007, VEL or VOX exposure in the pediatric population.

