In all pediatric age groups, the targeted exposures for SOF, GS-331007, VEL and VOX are the adult equivalent for which safety and efficacy has been established. Assuming similar variability for SOF, GS-331007, VEL or VOX AUC_{τ} in the pediatric population compared to adults, the predicted 90% confidence interval (CIs) of the geometric mean ratio (GMR) will be contained within the bounds of 50% to 200%.

Individual patient management will be performed by maintaining exposures comparable to adults. In the event more than one subject in each cohort exhibits SOF, GS-331007, VEL or VOX exposures (AUC_{τ}) less than the 2.5th percentile of adult values, a dose assessment may be required for the cohort as appropriate.

The effect of age and SOF/VEL/VOX FDC dose on PK (SOF, GS-331007, VEL and VOX) will be assessed.

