1.3. Sample Size and Power

Assuming similar variability for SOF, GS-331007, VEL, or VOX AUC_{tau} in the pediatric population compared to adults, a sample size of 20 pediatric subjects per cohort will provide at least 80% power to target a 90% confidence interval of the geometric mean ratio (GMR) within the bounds of 50% to 200% when comparing with the adult population.

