When the calculated HCV RNA value is within the linear range of the assay, then the result will be reported as the “<< numeric value>> IU/mL”. This result will be referred to in this document as the numeric result or as “≥ LLOQ detected” for categorical result.

When HCV RNA is not detected, the result is reported as “No HCV RNA detected” or “target not detected”. This result will be referred to in this document as “< LLOQ target not detected” or “< LLOQ TND”.

When the HCV RNA IU/mL is less than LLOQ of the assay, the result is reported as “< 15 IU/mL HCV RNA detected”. This result will be referred to in this document as “< LLOQ detected”.

The overall category of HCV RNA < LLOQ includes “< LLOQ TND” and “< LLOQ detected.”

For numerical HCV RNA data, values below LLOQ will be set to the LLOQ - 1 IU/mL (ie, 14 HCV RNA IU/mL). HCV RNA values returned as “No HCV RNA detected” will also be set to 14 IU/mL.

If methods based on the assumption that the data are normally distributed are not adequate, analyses may be performed on transformed data (eg, log₁₀ scale) or nonparametric analysis methods may be used, as appropriate.

Natural logarithm transformation will be used for plasma/blood concentrations and analysis of PK parameters. Plasma concentration values that are below the lower limit of quantitation (BLQ) will be presented as “BLQ” in the concentration data listing. Values that are BLQ will be treated as 0 at predose time points, and one-half the value of the LLOQ at postdose time points for summary purposes.

For the presentation of summary and order statistics, if at least 1 subject has a concentration value of BLQ for the time point, then the minimum value will be displayed as “BLQ” If more than 25% of the subjects have a concentration data value of BLQ for a given time point, then the minimum and Q1 values will be displayed as “BLQ” If more than 50% of the subjects have a concentration data value of BLQ for a given time point, then the minimum, Q1, and median values will be displayed as “BLQ” If more than 75% of the subjects have a concentration data value of BLQ for a given time point, then the minimum, Q1, median, and Q3 values will be displayed as “BLQ” If all subjects have concentration data values of BLQ for a given time point, then all order statistics (minimum, Q1, median, Q3, and maximum) will be displayed as “BLQ”.

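### The primary PK confidence interval comes from an ANOVA with no provision for unequal variances; against a much larger adult dataset it keeps its 90% level only if adolescents and adults are equally variable

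*SAP*

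**What the plan says.** SAP 8.1 (Population PK Analysis) states that the primary PK endpoint "will be evaluated by carrying out an analysis of variance (ANOVA) for log-transformed SOF, GS-331007, VEL and VOX" AUCtau, with 90% CIs for the ratios of geometric means. Protocol 8.5 agrees: "The primary endpoint of this analysis will be evaluated by carrying out an analysis of variance (ANOVA) for log-transformed SOF" and the other analytes. It identifies the comparator only by saying that "exposure data from this study will be compared to the integrated adult data", and it sets the equivalence bounds at 50% and 200%. Parts of SAP 8.1 are redacted, but the ANOVA and CI sentences are intact and match the protocol.

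Neither document names a variance structure or gives the number of adults. The nearest figure is in Protocol 1.4, where the combination "has been administered in Phase 2 and Phase 3 studies to over 1900 subjects". That counts people treated, not adults with an AUCtau.

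Equal variability appears only as a planning premise. SAP 1.3 opens with "Assuming similar variability for SOF, GS-331007, VEL, or VOX" AUCtau in the two populations, and Protocol 8.5 and 8.9 say the same. The one fallback on model assumptions, in SAP 3.6, concerns normality: "If methods based on the assumption that the data are normally distributed are not adequate, analyses may be performed on transformed data".

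Two other planned items bear on the point. SAP 8.1 also summarises pediatric exposures with the "geometric mean and its 95% confidence interval", %CV and SD. Protocol 8.5 has an individual-level check that begins "In the event more than one subject in each cohort exhibits SOF, GS-331007, VEL or VOX exposures" and refers to AUCtau below the 2.5th percentile of adult values. In that case the cohort's dose may have to be reassessed.

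**The concern.** Pooling is harmless when the groups are of similar size. It is not when one group is far larger, because the large group then determines the variance estimate while the small group supplies most of the sampling error of the difference. Here the small group is the one under study.

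This interval is the formal test of the primary endpoint, the adolescent exposure match that supports the dose. If adolescents are more variable than adults, the interval is too narrow and the test passes too easily near a bound. If they are less variable, it is too wide. The plan assumes similar variability when it sets the sample size, but nothing checks that assumption before the interval is built, and no alternative is specified if it fails.

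**Working it through.** **Inputs from the documents.** n = 20 adolescents (SAP 1.2 and 1.3; the final analysis in SAP 2.2 covers adolescents only); a two-sided 90% CI; bounds 0.5 and 2.0, which are ±ln 2 = ±0.693 on the log scale.

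**Assumed, because the documents do not give them.** Adult N from 20 to 1900; adult CV; and r, the adolescent/adult ratio of log-scale SDs, from 0.75 to 1.5. AUCtau is treated as independent lognormal values.

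**The plan's own figure.** The power of at least 80% (SAP 1.3) cannot be reproduced exactly without an SD, an adult N and a true ratio, but it is attainable. With a pooled analysis and true ratio 1.0, 80% power holds up to an adult CV of about 85% with 20 adults, 123% with 100 and 141% with 1000.

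**Where the variance estimate comes from.** The adult share of the residual degrees of freedom is (N − 1)/(N + 18): 99/118 = 84% at N = 100 and 1899/1918 = 99% at N = 1900.

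**Where the sampling error comes from.** At equal variances the adolescent share of the variance of the log ratio is (1/20)/(1/20 + 1/N): 0.05/0.06 = 83% at N = 100 and 0.05/0.05053 = 99% at N = 1900.

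**Effect on the standard error, adult SD set to 1.**
- True variance: r²/20 + 1/N.
- Expected pooled variance: [(19r² + N − 1)/(N + 18)] × (1/20 + 1/N).
- Example, r = 1.5 and N = 1900. True: 2.25/20 + 1/1900 = 0.1130. Pooled: (42.75 + 1899)/1918 × 0.05053 = 0.0512. The pooled SE is √(0.0512/0.1130) = 0.673 of the true SE. With t = 1.646 the effective multiplier is 1.646 × 0.673 = 1.107, and the normal probability within ±1.107 is about 73%.

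**Simulation**, pooled interval against Welch–Satterthwaite (100,000 replicates per cell; independent re-runs agree within simulation error). Coverage of the pooled 90% CI:

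| SD ratio r | 100 adults | 500 adults | 1900 adults |
|---|---|---|---|
| 0.75 | 95.2% | 96.8% | 97.0% |
| 1.0 | 90.3% | 90.1% | 90.0% |
| 1.25 | 84.5% | 81.7% | 81.2% |
| 1.5 | 79.5% | 74.3% | 73.2% |

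From 100 to 1900 adults, the one-sided error of the pooled interval at a bound is 8% to 9% at r = 1.25 and 10% to 13% at r = 1.5. Welch stays at about 90% coverage and 5% error throughout. With 20 adults the pooled interval covers about 90% at every r, so the imbalance is the cause.

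**Does the 2.5th-percentile check catch the false passes?** It was simulated for one analyte as at least 2 of 20 adolescents below the adult mean minus 1.96 SD, with r = 1.25 to 1.5 and adult log-SD 0.4 to 0.8.
- True ratio 0.5: the pooled CI passes with no trigger in 0.01% to 3.5% of studies.
- True ratio 2.0: it does so in 7% to 13%, against 3.5% to 5% with Welch.

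**Effect on the conclusion at true ratio 1**, r = 1.5, 1900 adults, with log-SD = √ln(1 + CV²):

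| Adult CV | Implied adolescent CV | Pooled passes | Welch passes |
|---|---|---|---|
| 40% | 63% | ≥ 99.9% | ≥ 99.9% |
| 60% | 100% | 99% | 95% |
| 100% | 194% | 83% | 54% |

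**The case against.** The size of the effect depends wholly on quantities the documents do not give. Adult N, adult CV and the SD ratio are all assumed, and 1900 is a count of people treated. With equal variances, or with about 20 adults, there is no problem; below a ratio of 1 the interval is conservative. Similar variability is a stated premise, so a one-variance ANOVA is at least consistent with the plan, and the plan never says that it pools. All of this stands. It limits the finding to a range.

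The widest gap, 83% against 54%, needs an adolescent CV of 194%. It also arises at a true ratio of 1, where passing is the right answer, so it is lost power under Welch and not a false conclusion under pooling. That is correct. At adult CV 60% and SD ratio 1.25 the gap is under one percentage point (99.8% against 99.2% with 1900 adults).

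The percentile check adds protection, and greater adolescent spread itself makes a trigger more likely: at true ratio 1, in 33% of studies at SD ratio 1.25 and 58% at 1.5, per analyte. It also applies to four analytes, where the simulation used one. But it looks only at low exposure, leaves a dose assessment optional, and is not carried into the SAP. It does little at the upper bound. On that side the protocol reports no exposure-safety relationship over a wide range of exposures in Phase 3, which lessens the clinical weight of a false pass there.

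The adolescent SD and %CV in SAP 8.1 would make a mismatch visible, but would not correct the interval. With children under 12 waived (SAP 2.2), no younger cohort's dose depends on this interval. Finally, AUCtau comes from a population model that uses sparse samples. Estimation error and shrinkage affect both methods, so Welch's exact performance holds only within the simulation's assumptions.

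**Conclusion.** The concern holds, conditionally. The plan tests its primary endpoint with an interval that has 90% coverage only if adolescents and adults are equally variable, once the adult dataset is much larger than 20, and it provides no alternative.

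Under assumed adult numbers of 100 to 1900, an SD ratio of 1.25 to 1.5 lowers coverage to between 84% and 73% and raises the one-sided error to between 8% and 13%. A ratio of 0.75 makes the interval too wide. These figures rest on assumed adult N, CV and SD ratio, and on lognormal AUCtau taken as observed.

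The documents do not show that the variances differ. The equivalence conclusion would rarely change with a true ratio near 1 and moderate variability. It is more exposed when variability is large or the true ratio lies near a bound, above all the upper one. Even where the conclusion stands, the reported interval may not have its stated level. This should be fixed because the correction is cheap and is best specified before the data are seen. Confidence is medium.

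**What to change.** In SAP 8.1, state that each geometric mean ratio and its 90% CI come from a model with a separate residual variance for each population and Satterthwaite degrees of freedom (Welch). In SAS this is PROC MIXED with a REPEATED statement and GROUP=population. Name the adult dataset and its N.

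This takes two sentences and one line of code. If the variances are equal, the mean interval width rises by 2.0% with 100 adults and 3.6% with 1900. Over the same range of adult numbers, Welch power at equal variances and true ratio 1 is about 90% to 95% at CV 100%, 80% to 87% at CV 120%, and 71% to just under 80% at CV 135%. At true ratio 0.8 it is 84% to 89% at CV 80% and 72% to 78% at CV 100%, where the pooled analysis gives 74% to 81%. The stated 80% power is therefore kept over much of the range in which the pooled analysis reaches it.

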10. SOFTWARE

SAS[®] Software Version 9.4. SAS Institute Inc., Cary, NC, USA.

11. SAP REVISION

Revision Date (DD MMM YYYY)	Section	Summary of Revision	Reason for Revision

12. APPENDICES

- Appendix 1. Study Procedures Table
- Appendix 2. Tanner Stages*
- Appendix 3. PedsQL™ Score Calculation Algorithms

Appendix 1. Study Procedures Table

Appendix Table 1. Screening and On-Treatment Study Visits

	Screening	Day 1 ^a	On-Treatment Study Week (±3 Days)					Early Termination ^a
			Week 1	Week 2 ^{b,v}	Week 4 ^s	Week 8 ^b	End of Treatment ^c	
Clinical Assessments								
Informed Consent/Assent	X							
Determine Eligibility	X	X						
Medical History	X							
Parental Height, if known		X						
Complete Physical Examination	X	X					X	X
Symptom Directed Physical Examination			X	X	X	X		
Tanner Pubertal Stage Assessment		X					X	X
Vital Signs ^d	X	X	X	X	X	X	X	X
Body Weight and Height	X	X	X	X	X	X	X	X
Radiographic Bone Age Assessment		X					X	X
AEs and Concomitant Medications	X ^e	X	X	X	X	X	X	X
FibroScan [®] (if available)	X ^f	X ^f						
Pregnancy Prevention Counseling ^g		X			X	X	X	X
SOF/VEL/VOX Swallowability Assessment	X ^h	X ^h						
SOF/VEL/VOX Acceptability Questionnaire ⁱ		X					X	X
Quality of Life Survey ^j		X					X	X
Review of Study Medication Compliance				X ^k	X	X	X	X
Study Drug Dispensing		X			X	X		
Return of Study Drug Bottles					X	X	X	X
Review Dosing Diary				X ^k	X ^k			

	Screening	Day 1 ^a	On-Treatment Study Week (±3 Days)					End of Treatment ^c	Early Termination ^a
			Week 1	Week 2 ^{t,v}	Week 4 ^s	Week 8 ^b			
Laboratory Assessments									
Hematology, Chemistry	X	X	X	X	X	X	X	X	
Coagulation	X	X					X	X	
HCV RNA	X	X	X	X	X	X	X	X	
HBV DNA ^l		X	X	X	X	X	X	X	
Viral Sequencing ^m		X	X	X	X	X	X	X	
Serum or Urine Pregnancy Testing ⁿ	X	X		X ^o	X	X	X	X	
Single sparse PK sample collected at anytime			X			X	X	X	
Two sparse PK Samples collected pre dose and between 15 minutes and up to 4 hours postdose				X ^p	X ^p				
CCI									
Pharmacogenomics Sample ^f		X	X	X	X	X	X	X	
Urinalysis	X	X		X ^k	X ^k				
Urine Drug Screen	X								
IL28B Genotyping	X ^f	X ^f							
Bone Age Biomarkers		X						X ^w	
HCV Genotyping	X								
HIV testing, HAV Antibody, HCV Antibody, HBsAg, HBsAb, HBcAb	X								
HbA1c, Fibrotest [®] , APRI	X								
TSH	X						X	X	
Alpha 1 anti trypsin	X								

	Screening	Day 1 ^a	On-Treatment Study Week (±3 Days)					Early Termination ^a
			Week 1	Week 2 ^{u,v}	Week 4 ^s	Week 8 ^b	End of Treatment ^c	
Approximate amount of blood drawn (mL) Cohort 1	22.1	12.3	9.3	11.3 (no IPK) 23.3 (if IPK) ^s	11.3	9.3	13.2	16.8
Approximate amount of blood drawn (mL) Cohort 2	22.1 ^u	12.3	9.3	18 ^t	11.3	9.3	13.2	16.8
Approximate amount of blood drawn (mL) Cohort 3	22.1 ^u	12.3	8.3	8 ^v	9.3	8.3	12.2	12.2

- a Subjects should be instructed to fast (no food or drink, except water), starting from midnight (00:00) or earlier, as appropriate, on the evening prior to Day 1 and Early Termination (if applicable) to ensure an approximate 8 hour fast prior to the blood sample collection the next morning.
- b The Week 8 Visit will only be completed for subject DAA naive with cirrhosis or DAA experienced with or without cirrhosis, who are on 12 weeks of treatment.
- c For subjects that are DAA naive without cirrhosis, who are on 8 weeks of treatment, the End of Treatment visit will occur at Week 8. For subjects that are DAA naive with cirrhosis or DAA experienced with or without cirrhosis, who are on 12 weeks of treatment, the End of Treatment Visit will occur at Week 12.
- d Vital signs include blood pressure, pulse, respiratory rate, and temperature.
- e From the time of obtaining informed consent through the first administration of investigational medicinal product, record all serious adverse events (SAEs), as well as any adverse events related to protocol mandated procedures.
- f FibroScan[®] and IL28B genotyping may be performed at Day 1 if not completed at Screening.
- g Including partner pregnancy prevention for male participants (all subjects ≥ 12 years old and subjects < 12 years old at the discretion of the Investigator based on subject's pubertal status).
- h Swallowability may occur at Day 1 if not completed during Screening.
- i A questionnaire will be administered to subjects to assess acceptability, including palatability, on Day 1, EOT (Week 8 or Week 12), or Early Termination (as applicable). If the subject is unable to complete the questionnaires, the parent/legal guardian will assist to complete the questionnaire. The subjects' parent/legal guardian will also complete a questionnaire on EOT (Week 8 or Week 12) or Early Termination (as applicable).
- j Quality of life survey will be completed by all subjects and their parent/legal guardian. Subject and parent/legal guardian is to review questionnaire and write/mark answers directly onto the questionnaire.
- k **CCI** [REDACTED]
- l HBV DNA testing for subjects HBcAb positive at Screening.
- m Plasma samples will be collected and stored for potential HCV sequencing and other virology studies. **CCI** [REDACTED]
- n All females of childbearing potential will have a serum pregnancy test at Screening. In addition, all females of childbearing potential will perform a urine pregnancy test at Day 1 and every 4 weeks during the dosing period and for a minimum of 30 days following the last dose of SOF/VEL/VOX FDC.
- o [REDACTED]

- p Two sparse PK samples collected pre dose and between 15 minutes and 4 hours postdose CCI [REDACTED]
- r Only for subjects that have provided consent, an appropriate blood sample for PG analysis will be collected at Day 1. If the sample was not collected Day 1 visit, the sample may be drawn at subsequent visits CCI [REDACTED]
- u In cohort 2 and cohort 3, for subject weighing ≤ 25 kg, the screening visit will be performed in two different days. Samples for chemistry, hematology, coagulation, TSH, HIV/HAV/HCV testing will be performed on one day (12 ml of blood will be collected) and all other samples including for HCV RNA, HCV genotype and IL28B will be collected on a different day within the screening window (10.1 ml of blood will be collected). If the subject's weight is > 25 kg, the screening visit blood draw can be completed in one day. [REDACTED]
- w In cohort 3, Bone age biomarkers (CTX and PINP) samples will not be collected at the Early Termination visit

